## 6.3. Population for Analysis

Safety and efficacy analyses will be conducted on all patients who have received at least one dose of the study treatment(s), regardless of whether they are deemed evaluable for the assessment of a dose level.

Pharmacokinetic (PK) analyses will be conducted on patients who have received at least one dose of the study treatment(s) and have sufficient samples collected to allow the estimation of LY2510924 and MEDI4736 PK parameters.

Pharmacodynamic (PD) analyses will be conducted on subjects who have received at least one dose of the study treatment(s) and have sufficient samples collected to allow the assessment of PD.

## 6.4. Patient Disposition

A detailed description of patient disposition will be provided. It will include summaries of the number and percentage of patients entered into the study, enrolled in the study, completing the study, and reasons for discontinuation from study treatment, as well as discontinuation from the study. Patients completing the study are defined as patients who received one cycle of study treatment or discontinued prior to doing so due to an AE classified as a DLT in Phase 1a and patients who received two cycles of study treatment in Phase 1b. All patients entered in the study will be included in the summary. Reason for discontinuation from both study treatment

and the study will be listed by the pre-determined categories. If the reason for discontinuation is adverse event (AE) or death, the associated AE or cause of death will be reported.

Screen failures will be listed and summarized if appropriate.

## 6.5. Patient Characteristics

Patient characteristics will be summarized and listed for all patients enrolled and will include:

- Patient demographics, including age, sex, race, ethnicity, screening height and weight, and screening body mass index (BMI).
- Baseline disease characteristics, including initial pathological diagnosis, basis for initial diagnosis, disease stage at initial diagnosis and Eastern Cooperative Oncology Group (ECOG) performance status.
- Prior disease-related therapies including systemic, radiotherapy, and cancer surgeries, if known, including dose, best response, date of progression.
- Historical substance consumption such as alcohol and tobacco use.

Other patient characteristics will be summarized and listed as deemed appropriate.

## 6.6. Treatment Compliance

### 6.6.1. *LY2510924 Compliance*

Patient compliance with LY2510924 will be assessed on Day 1 of each cycle (excluding Cycle 1). Compliance will be assessed by direct questioning, review of diary, and counting any returned vials. Patients are considered significantly noncompliant if <75% of expected study drug is taken in a visit interval. Deviations from the prescribed dosage regimen should be recorded on the CRF. On those study days that PK collection is scheduled, patients will wait to self-administer LY2510924 until they are in the clinic. For more details refer to Protocol Section 7.6.1.

### 6.6.2. *MEDI4736 Compliance*

MEDI4736 will be administered intravenously at the investigational site, under the direction of the investigator. As a result, a patient's compliance with study drug administration is ensured. Patients should attend scheduled clinic visits and must comply with study criteria under their control. Deviation(s) from the prescribed dosage regimen should be recorded on the CRF.

## 6.7. Concomitant Therapy

All medications will be coded to the generic preferred name according to the current World Health Organization (WHO) drug dictionary. All concomitant medications will be listed and summarized using the preferred name by cohort and overall for all patients on therapy. If the concomitant medication use is due to an adverse event (AE), the associated National Cancer Institute's (NCI) Common terminology Criteria for Adverse Events (CTCAE) Version 4.0 term will be listed.

## 6.8. Safety Analyses

All patients who receive at least one dose of LY2510924 or durvalumumab will be evaluated for safety and toxicity. The National Cancer Institute Common Terminology Criteria for Adverse Events Version 4.0 (NCI-CTCAE v4.0) will serve as the reference document for choosing appropriate terminology for, and grading the severity of, all adverse events (AEs) and other symptoms.

Safety analyses will include summaries of the following:

- adverse events, including severity and possible relationship to study drug
- DLTs at each dose level
- dose adjustments
- laboratory values
- vital signs
- ECG readings
- transfusions

### 6.8.1. Extent of Exposure

Study drug exposure information will be summarized by cohort and overall for patients on therapy, including cycles received per subject, duration on therapy, and cumulative dose.

Dose adjustment information will be summarized by cohort and overall for patients on therapy, including dose reductions, dose delays, dose omissions, dose increases, and the reasons leading to dose adjustments.

Dose intensity, defined as the actual amount of drug taken per week, and relative dose intensity, defined as the actual amount of drug taken/planned amount of drug taken $\times$ 100%, will also be summarized by cohort and overall.

### 6.8.2. Dose Limiting Toxicity

Dose limiting toxicities (DLTs) will be summarized and listed by cohort and overall for the safety population.

DLT-equivalent toxicities will also be summarized and listed by cohort and overall for the safety population.

### 6.8.3. Adverse Events

AE terms and severity grades will be assigned by the investigator using CTCAE Version 4.0. Any minor version of CTCAE Version 4.0 (for example, CTCAE Version 4.03) may be used for this study. In addition, AE verbatim text will also be mapped by the sponsor or designee to corresponding terminology within the Medical Dictionary for Regulatory Activities (MedDRA) dictionary. AEs will be reported using a unified CTCAE/MedDRA reporting process:

- The CTCAE v4.0 term reported by the investigator will be mapped to the MedDRA preferred term (PT) and system organ class (SOC) of the corresponding MedDRA lowest level term (LLT), unless the reported CTCAE term is “Other-specify”.

- If the reported CTCAE term is “Other-specify” the MedDRA LLT, PT and SOC mapped from the verbatim AE term will be used
- All listings and summaries will use the CTCAE terms when available or the MedDRA LLT, along with the MedDRA PT resulting from this process.

A treatment emergent adverse event (TEAE) is defined as any AE that begins on or after the day of the first dose of study treatment or any pre-existing condition that increases in CTCAE grade on or after the day of the first dose of study treatment, and prior to the end of the short-term (safety) follow-up. Comparisons of pre-existing conditions to treatment events at the LLT level will be used in the treatment-emergent computation.

The number of patients who experienced a TEAE, SAE, or TEAE possibly related to study drug, will be summarized. TEAEs will be summarized by SOC, by PT terms of decreasing frequency within SOC, and by maximum CTCAE grade and “Any grade” categories. Immune-related AEs may be tabulated if deemed appropriate.

Historical illnesses are defined as events which ended before completion of the screening visit. Pre-existing conditions are defined as AEs that begin but do not resolve prior to the first dose of study drug is administered. The pre-existing conditions will be presented by patient and can be combined with the adverse event listing, so that the history of the pre-existing conditions/adverse events can be traced. Historical illnesses and pre-existing conditions will be summarized and listed by cohort and overall for all patients on therapy.

#### **6.8.3.1. Adverse Events of Special Interest for Durvalumab**

AESIs for durvalumab include infusion-related reactions and immune-related AEs: colitis; pneumonitis; hepatotoxicity: ALT/AST increases/hepatitis/hepatotoxicity; neuropathy/neuromuscular toxicity; endocrinopathy; dermatitis; nephritis; and pancreatitis.

#### **6.8.4. Deaths, Other Serious Adverse Events, and Other Notable Adverse Events**

A summary of deaths will be presented by cohort and overall. Reasons for death will be summarized separately for deaths on therapy, within 30 days of discontinuation of study therapy and after 30 days of discontinuation of study therapy. Other listings include:

- Listing of Deaths
- Listing of Serious Adverse Events
- Listing of Subjects who Discontinued due to Adverse Events of Death

#### **6.8.5. Clinical Laboratory Evaluation**

Laboratory data (including abnormal laboratory data) will be listed by cycle for all patients on therapy. In addition to the investigator-reported AEs, relevant hematology and chemistry laboratory values will be graded according to CTCAE v4.0. These abnormal lab parameters with derived CTCAE grades will be summarized by visit and cohort.

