8.1. Safety Evaluations

Safety is the primary endpoint of this Phase 1a/b study as determined by the NCI CTCAE v 4.03. All patients who receive at least 1 dose of LY2510924 or durvalumab will be evaluated for safety as measured by the occurrence of AEs, SAEs, deaths, and laboratory abnormalities, assessed during treatment and for 90 days in follow-up.

Patients will have regularly scheduled study visits at the clinical site as noted in [Attachment 1](#), where safety assessments including AE collection, laboratory assessments, vital sign collection, and physical examinations will be performed.

Imaging studies will be performed every 8 weeks or sooner if clinically indicated. Liver function, as part of the routine clinical chemistry panel, will be tested every other week in Cycle 1 and every cycle thereafter.

Study procedures and their timing are described in the Study Schedule ([Attachment 1](#)). [Attachment 2](#) lists the specific tests that will be performed for this study.

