Attachment 2. Protocol CXAD Clinical Laboratory Tests

Clinical Laboratory Tests

Hematology^b

Hemoglobin
Hematocrit
Mean corpuscular hemoglobin
Mean corpuscular hemoglobin concentration
Mean corpuscular volume
Erythrocyte count (RBC)
Leukocytes (WBC)
Neutrophils^c (% and absolute)
Lymphocytes (% and absolute)
Monocytes (% and absolute)
Platelets
Eosinophils
Basophils

Coagulation^b

aPTT
PT
INR

Urinalysis^b

Bilirubin
Blood
Color and appearance
Glucose
Ketones
pH
Protein
Specific gravity
Urine leukocyte esterase

Clinical Chemistry^a

Serum Concentrations of:

Sodium
Magnesium
Chloride
Phosphorus
Potassium
Total and direct bilirubin
Alkaline phosphatase
Alanine aminotransferase
Aspartate aminotransferase
Bicarbonate
Blood urea nitrogen
Creatinine
Total protein
Calcium
Glucose, random
Albumin

Clinical Chemistry^d

Serum Concentrations of:

Lactate dehydrogenase (LDH)
Lipase
Gamma glutamyl transferase (GGT)
Creatine kinase
Amylase

Thyroid Function Tests^b

Thyroid stimulating hormone
Free thyroxine (fT4)

Hepatitis B (HBsAg, Anti-HBc)^b

Hepatitis C (Anti-HCV, HCV RNA)^b

HIV^b

Urine or serum (β -human chorionic gonadotropin
(β -hCG) **Pregnancy Test** (females only)^b

Clinical Laboratory Tests

Abbreviations: aPTT = activated partial thromboplastin time; CRF = case report form; HBsAg = hepatitis B surface antigen; HBc = hepatitis B core antibody; HCV = hepatitis C virus; INR = international normalized ratio of prothrombin time; PT = prothrombin time; RBC = red blood cells; RNA = ribonucleic acid; WBC = white blood cells.

- a Local chemistry laboratory testing will be used to determine patient eligibility and decisions for treatment. Central chemistry laboratory testing will also be performed, and will be used for data analyses.
- b Local or investigator-designated laboratory. Treatment decisions will be based on local laboratory results.
- c Neutrophils reported by automated differential hematology instruments include both segmented and band forms. When a manual differential is needed to report the neutrophils, the segmented and band forms should be added together and recorded on the CRF, unless the CRF specifically provides an entry field for bands.
- d Centrally only.

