	
Grade 3 or 4 (Grade 3: stool frequency of ≥ 7 over baseline per day;
 
Grade 4: life threatening consequences)
	Permanently discontinue study drug/study regimen.	
For Grade 3 or 4:
 
 – Promptly initiate empiric IV methylprednisolone 2 to 4 mg/kg/day or equivalent. – Monitor stool frequency and volume and maintain hydration. – Urgent GI consult and imaging and/or colonoscopy as appropriate. – If still no improvement within 3 to 5 days of IV methylprednisolone 2 to 4 mg/kg/day or equivalent, promptly start further immunosuppressives (eg infliximab at 5 mg/kg once every 2 weeks). Caution: Ensure GI consult to rule out bowel perforation and refer to infliximab label for general guidance before using infliximab. – Once the patient is improving, gradually taper steroids over ≥ 28 days and consider prophylactic antibiotics, antifungals, and anti-PCP treatment (refer to current NCCN guidelines for treatment of cancer-related infections [Category 2B recommendation]).^a

Hepatitis (elevated LFTs)
 
Infliximab should not be used for management of immune-related hepatitis.
	Any Grade	General Guidance	
For Any Grade:
 
 – Monitor and evaluate liver function test: AST, ALT, ALP, and TB. – Evaluate for alternative etiologies (eg, viral hepatitis, disease progression, concomitant medications).
	Grade 1 AST or ALT $> 3 \times$ ULN and/or TB $>$ to $1.5 \times$ ULN)	No dose modifications. 
 • If it worsens, then treat as Grade 2 event. 	
For Grade 1:
 
 – Continue LFT monitoring per protocol.
	Grade 2 (AST or ALT > 3 to $5 \times$ ULN and/or TB > 1.5 to $3.0 \times$ ULN)	Hold study drug/study regimen dose until Grade 2 resolution to Grade ≤ 1 . 
 • If toxicity worsens, then treat as Grade 3 or Grade 4. • If toxicity improves to Grade ≤ 1 or baseline, resume study drug/study 	
For Grade 2:
 
 – Regular and frequent checking of LFTs (eg, every 1 to 2 days) until elevations of these are improving or resolved. – If no resolution to Grade ≤ 1 in 1 to 2 days, discuss with study physician. – If event is persistent (> 3 to 5 days) or worsens, promptly start

Specific Immune-mediated Reactions

Adverse Events	Severity Grade of the Event (NCI CTCAE version 4.03)	Dose Modifications	Toxicity Management

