### **6.8.7. Electrocardiograms**

Electrocardiogram (ECG) data will be summarized by visit and parameter for patients on therapy. Any abnormal ECG data will be listed by patient. Number and percentage of subjects with AEs that could be associated with abnormal ECGs will be presented, if appropriate.

If available, the number of patients meeting the following criteria with respect to QTc will be presented for maximum on-study value:

- QTc, >480 to 500 msec, and >500 msec and delta QTc >30 to 60 msec, and >60 msec.

All instances when a patient met the above criteria will be listed. Maximum absolute and change from baseline QTc data will be summarized as a continuous variable. Frequency of patients with Normal ( $\leq 480$  msec) or High ( $>480$  msec) QT/QTc interval at baseline and post baseline nominal time points will be summarized by shift table. Summaries of other ECG parameters (for example, RR, PR, and QRS) will be presented, if appropriate. A QT-concentration analysis of change from baseline in QTcF versus serum concentration may be performed, if deemed appropriate.

Lilly will review ECG data and monitor cardiac events/deaths during the course of the study.

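### SAP 6.8.5 tabulates derived laboratory grades only by visit and cohort, so no table gives the number of patients who ever reach each grade, and local-only chemistry peaks have no stated route into that summary

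*SAP*

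**What the plan says.** Protocol 8.1 names safety as the primary endpoint, "measured by the occurrence of AEs, SAEs, deaths, and laboratory abnormalities", followed through treatment and for 90 days afterwards.

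SAP 6.8.5 provides three things:
- a listing: "Laboratory data (including abnormal laboratory data) will be listed by cycle for all patients on therapy"
- grading: "relevant hematology and chemistry laboratory values will be graded according to CTCAE v4.0", which it describes as additional to the adverse events that investigators report
- one summary of those grades: "These abnormal lab parameters with derived CTCAE grades will be summarized by visit and cohort"

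Protocol 10.4 adds only that laboratory values will be summarised. Neither document mentions a per-patient maximum grade, a baseline-to-worst shift table for laboratory values, or a rule for unscheduled draws.

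On the source of results, Protocol Attachment 2, footnote a, uses local chemistry for eligibility and treatment decisions, then says: "Central chemistry laboratory testing will also be performed, and will be used for data analyses". Hematology carries footnote b: "Local or investigator-designated laboratory. Treatment decisions will be based on local laboratory results".

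For QTc, by contrast, SAP 6.8.7 counts patients in each category and says that these counts "will be presented for maximum on-study value". It also plans a shift table.

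**The concern.** The natural safety question in a small single-arm cohort is how many patients ever reached Grade 3 or higher on a given analyte. SAP 5.1 justifies 15 patients per expansion arm by the precision of a proportion of patients. A by-visit table answers a different question: how many were abnormal at that visit. The rows cannot be added up, because one patient may appear in several of them, and no single row gives the total.

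The protocol also generates results between visits. For Grade 2 hepatitis, Attachment 11 asks for "Regular and frequent checking of LFTs (eg, every 1 to 2 days" or so, and Table CXAD.7.2 asks for white cell and neutrophil rechecks every 2 to 3 days after leukocytosis. The SAP does not say where such results go. For chemistry the choice of laboratory matters too: if the between-visit sample was run only locally, footnote a points the analysis to a central result that does not exist for that draw.

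At stake is whether the report can state per-patient laboratory toxicity from objective grades, independently of what investigators chose to report as adverse events.

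**Working it through.** **1. The plan's own figure.** SAP Table CXAD.5.1 gives exact 95% limits for x cases in n = 15. With lower limit = Beta quantile(0.025; x, n−x+1) and upper limit = Beta quantile(0.975; x+1, n−x):

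| x/15 | Recomputed | Table |
|---|---|---|
| 0 | 0 to 0.218 | 0.0 to 0.22 |
| 3 | 0.043 to 0.481 | 0.04 to 0.48 |
| 6 | 0.163 to 0.677 | 0.16 to 0.68 |
| 9 | 0.323 to 0.837 | 0.32 to 0.84 |

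The table reproduces. Its unit is the patient.

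**2. What by-visit rows can and cannot show (assumed data).** Suppose four visits each show one Grade 3 value among 15 patients, so each row reads 1/15 = 6.7%.
- If it is the same patient each time, per-patient incidence is 1/15 = 6.7% (exact 95% CI 0.2% to 31.9%).
- If it is four different patients, it is 4/15 = 26.7% (exact 95% CI 7.8% to 55.1%).

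The by-visit table is identical in both cases.

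**3. How often a scheduled draw meets a short excursion.** Protocol 8.1 schedules liver tests every other week in Cycle 1 and once per cycle after that, so the gaps are about 14 and 28 days. Attachment 1 adds hematology and chemistry at the 30-, 60- and 90-day follow-up visits. Assume an excursion of d days with onset uniform over the gap. The chance that a scheduled draw falls inside it is min(1, d/gap):

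| Duration | 14-day gap | 28-day gap |
|---|---|---|
| 3 days | 21% | 11% |
| 7 days | 50% | 25% |
| 14 days | 100% | 50% |
| 21 days | 100% | 75% |

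The durations are assumptions; the documents give none. A draw inside an excursion also need not catch its peak.

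**4. Which analytes the laboratory-source problem touches (Attachments 2 and 3).**
- Footnote a chemistry (including ALT, AST, bilirubin and creatinine): tested locally and centrally, with central used for analysis. Affected when a draw has no central result.
- Hematology, coagulation, urinalysis and thyroid tests: footnote b, local, with no central source named. Not affected by source. Graded hematology still lacks a per-patient maximum.
- LDH, lipase, GGT, creatine kinase and amylase: central only. No local peak to lose.
- Optional hepatic work-up in Attachment 3: most tests go to a sponsor-designated laboratory, so some between-visit liver results are not local.

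**The case against.** A reader might infer that between-visit peaks never reach a laboratory table. The documents do not support that. SAP 6.8.5 says by visit; it does not say scheduled visits only. It is silent on whether unscheduled draws are dropped, shown separately or mapped to a visit. A worst value that falls on a scheduled visit does appear in that row, though it is not marked as the patient's maximum. Nor do the documents say which laboratory's results define a DLT; they tie local results to eligibility and treatment decisions.

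The strongest counter-argument is that important peaks are counted elsewhere. Protocol 8.1.2 requires clinically significant laboratory findings to be reported as adverse events, and SAP 6.8.3 tabulates treatment-emergent events by maximum grade. DLTs, which include laboratory criteria, and DLT-equivalent toxicities are summarised by cohort and overall (SAP 6.8.2). Reasons for dose adjustment are summarised (SAP 6.8.1). With about 15 patients per arm, a reader could count affected patients from the listing.

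Much of this stands, and it limits the harm. It does not close the gap. Adverse event reporting turns on the investigator's view of significance. The DLT definition in Protocol 7.2.2.1 requires judged relatedness and carries exclusions. A listing is not an incidence, and counting by hand recovers only the results that were listed. SAP 6.8.5 itself sets derived grading alongside reported events as a separate measure.

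It is also fair to say that the 1-versus-4 example takes the two extremes, that one patient's repeated results are likely to be correlated, and that the SAP defines no visit denominator. The example shows what the table cannot distinguish and nothing more.

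**Conclusion.** The point holds in a limited form. As written, the plan does not tabulate the number of patients ever reaching each derived laboratory grade, although laboratory abnormalities belong to the primary safety endpoint and the same SAP uses a per-patient maximum for QTc. For the footnote a chemistry panel only, a peak seen solely on a local between-visit draw has no stated route into the graded summary.

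The size of the effect in this trial cannot be derived from the documents. On the assumed data above, the same by-visit rows fit a per-patient incidence anywhere from 6.7% to 26.7%. A monthly draw would meet a 7-day excursion about a quarter of the time if onset is uniform.

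This is a cheap, worthwhile improvement to a descriptive analysis. It is not evidence that serious laboratory toxicity would go unreported.

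**What to change.** Add to SAP 6.8.5 a table of maximum post-baseline CTCAE grade per patient for each graded analyte, with shift from baseline grade, by cohort or arm and overall, through the 90-day safety follow-up. The shift matters because inclusion criterion 6 admits patients with liver involvement at transaminases up to 5 × ULN, which Attachment 11 labels Grade 2 from above 3 × ULN.

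State two rules with it:
- Scheduled and unscheduled results both count.
- For the footnote a panel, use the central result where one exists and the local result only when that draw has no central result. Taking the worse of a paired local and central result would bias grades upward.

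Keep the by-visit table as supportive, and say how unscheduled draws appear in it.

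The cost is one extra table, plus bringing local chemistry with its reference ranges into the analysis dataset. The data handling is the larger part. No visit, sample or clinical rule changes.
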